9.2.2.5 Analysis of the secondary judgement criteria

All AE and SAE will be coded with MedDRA. Each adverse event observed between inclusion and the end of follow-up will be listed by frequency in each group. Then, the percentage of patients with at least one adverse event, or at least one severe adverse event will be computed and compared between the 2 groups. A list and verbatim of severe adverse events will be provided. All analyses will be performed on the safety population.

Efficacy criteria:

- The total duration of nosebleeds will be presented in each group for the 3 periods (6 weeks before treatment, 6 weeks of treatment, 6 weeks' follow-up after treatment). The relative evolution in duration of nosebleeds will be computed by subtracting the baseline value from the V2 value (end of treatment) and the V3 value (end of study). The delta from inclusion (V3/V1 & V2/V1) in total duration will be compared between the 2 groups using student t-tests (or

Mann-Withney tests in case of non normality). Mixed models will be produced to compare evolution between the groups.

- The number of nosebleeds will be presented in each group for the 3 periods (6 weeks before treatment, 6 weeks of treatment and 6 weeks' follow up after the end of treatment). The relative evolution in duration of nosebleeds will be computed by subtracting the baseline value from the V2 value (end of treatment) and the V3 value (end of study). The delta (V3/V1 & V2/V1) in number will be compared between the 2 groups using student t-tests (or Mann-Withney tests in case of non normality). Mixed models will be produced to compare evolution between the groups.
- The number of red blood cell transfusions will be presented in each group for the 3 periods (6 weeks before treatment, 6 weeks of treatment, 6 weeks' follow-up after treatment). The relative evolution in the number of red blood cell transfusions will be computed by subtracting the baseline value from the V2 value (end of treatment) and the V3 value (end of study). The delta (V3/V1 & V2/V1) in number of red blood cell transfusions will be compared between groups using student t-tests (or Mann-Withney tests in case of non normality). Mixed models will be produced to compare the evolution between groups.
- The physical component and mental component of the SF36 and its domains will be presented in each group at inclusion, at the end of the treatment and at the end of the study. The relative evolution in SF36 (overall and per item) will be computed by subtracting the baseline value from the V2 value (end of the treatment) and the V3 value (end of the study). The delta (V3/V1 & V2/V1) in components and in each SF36 domain will be compared between groups using student t-tests (or Mann-Withney tests in case of non normality). Mixed models will be produced to compare evolution between the groups.
- The ESS will be presented for each group at inclusion, at the end of the treatment, and at the end of the study. The relative evolution in ESS will be computed by subtracting the baseline value from the V2 value (end of treatment) and the V3 value (end of study). The delta (V3/V1 & V2/V1) in ESS will be compared between groups using student t-tests (or Mann-Withney tests in case of non normality). Mixed models will be produced to compare evolution between the groups.
- The biological values (hemoglobin and serum ferritin) will be presented in each group at inclusion, the end of the treatment and the end of the study. The relative evolution in hemoglobin and ferritine levels will be computed by subtracting the baseline value from the V2 value (end of treatment) and the V3 value (end of study). The delta (V3/V1 & V2/V1) in biological measures will be compared between groups using student t-tests (or Mann-Withney tests in case of non normality). Mixed models will be produced to compare the evolution.

Systemic tacrolimus Tacrolimus systemic absorption: the percentage of patients who present with systemic absorption of KK506 will be calculated. If tacrolimus is detected in the blood the level of exposure will be listed.

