1.3.3 Safety: Ointment safety

1.3.3.1 Skin

No major safety concerns have been reported to date. Tacrolimus ointment is generally well-tolerated, the primary adverse events being mild to moderate and transient application-site reactions: skin burning, pruritus and erythema.³⁶⁻⁴⁰

Approximately 50% of patients experienced some type of skin irritation adverse reaction at the site of application. Burning sensation, pruritus, and erythema were very common, usually mild to moderate in severity and tended to resolve within one week of starting treatment. Increased skin sensitivity and skin tingling were also common skin irritation adverse reactions. Alcohol intolerance (facial flushing) was common. Patients may be at an increased risk of folliculitis, acne, and herpes simplex.³⁶

Three published observational studies have assessed the carcinogenic risk on large cohorts of patients:

- The retrospective Arana study (2010)⁴¹ compared the incidence of cancer in the general population and in patients with atopic dermatitis. It focused on a cohort of 4,456,008 patients with no history of cancer from "The Health Improvement Network" database, representative of the population of the United Kingdom. This study showed a higher incidence of skin cancer in atopic patients, but it did not make it possible to establish a link between skin cancer and treatment for atopic dermatitis.
- Hui (2009)⁴² studied safety in a retrospective cohort. Of the 11,961 cancer cases reported between 2001 and 2005, no difference was observed for all forms of cancer combined between patients exposed or not exposed to calcineurin inhibitors after adjustment according to age and sex.
- Schneeweiss⁴³ studied a cohort of 1,252,300 patients, to assess the risk of lymphoma during treatment with tacrolimus, pimecrolimus or corticosteroids. Compared to the general population, these three treatments were associated with an increased risk of occurrence of lymphoma. Compared to patients with untreated

atopic dermatitis, however, the three treatments were not associated with an increased risk of lymphoma.

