2.3 Rationale for the methodology

The methodology retained for this efficacy (phase II) study is a randomized trial, which is the design presenting the highest level of evidence.

We started to assess parameters by comparing data collected at 3 visits:

- Visit 1: inclusion, data collected for 6 weeks before treatment and during the visit
- Visit 2: end of treatment, data collected during the 6 weeks preceding the visit (i.e. 6 weeks of treatment) and during the visit
- Visit 3: end of study, data collected during the 6 weeks preceding the visit (i.e. 6 weeks following the end of treatment) and during the visit.
- In addition, data are collected on pharmacokinetic at Day 8 and Day 22 (blood sample) and on safety at Day 15 and Day 31 (phone call).

[figure not shown]

Figure 4 General diagram of the study

For safety reasons, as no tolerance data are available with a nasal administration, we decided to include patients sequentially. We designed an inclusion scheme in 3 or 4 steps. An independent safety committee will give its recommendations on the continuation of the study.

The theoretical inclusion scheme is described as follows. It was established pragmatically based on our sample size.

We consider that a cessation of treatment for at least 8 consecutive days, for safety concern, that is to say adverse reaction due to the ointment, is a major issue.

- **STEP 1- 8 patients will be included in Lyon.**

On day 31 (phone call): information regarding adverse events (AE), severe adverse events (SAE) and observance of the treatment for the first 30 days of treatment are collected for these 8 patients.

Based on these data, a DSMB meeting (#1) will be consulted and will give its recommendations on the continuation of the study according to the following theoretical scheme:

Number of patient who stop treatment for 8 consecutive days		ARM PLACEBO				
		0	1	2	3	4
ARM ACTIV	0	0	1	2	3	4
	1	1	2	3	4	5
	2	2	3	4	5	6
	3	3	4	5	6	7
	4	4	5	6	7	8

The numbers inside the table = total number of events in both arms

	No imbalance between arms
	Imbalance between arms active>placebo
	Imbalance between arms placebo>active
	+ 16 patients
	+ 8 patients
	Stop

If there is no imbalance between arms (difference ≤ 1), the total number of patient who stop treatment at least 8 consecutive days will be consider (semi-blind data transmitted to DSMB):

- < 4 patients in both arms \rightarrow inclusion of 16 new patients (Step 2A)

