3.2 Secondary objectives

The secondary objectives are to evaluate:

4. Tolerance of tacrolimus nasal administration for 6 weeks, throughout the study.

5. Efficacy of the treatment on progress in the

- clinical parameters:
 - Nosebleed duration,
 - Number of nosebleeds,
 - Number of transfusions of red blood cells.
 - Quality of life
 - ESS = Epistaxis Severity Score

- biological parameters: hemoglobin and serum ferritin concentrations

These parameters will be evaluated at the end of the 6 weeks of treatment (V2) and at the end of 6 weeks of follow-up (V3).

6. Systemic absorption after nasal administration.

4 Methodology

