9.2.2.4 Analysis of the main judgement criterion

The percentage of patients experiencing improvement in their nosebleeds will be computed in each group. An improvement is defined as a 30% reduction in the total duration of nosebleeds over 6 weeks after treatment, compared with the duration of the nosebleeds in the 6 weeks before the treatment.

The percentage of the two groups will be compared using a Fisher exact test, and the analysis will be performed on the intention to treat population.

Patients who stopped the treatment but who have epistaxis grids will be analyzed using their data. Patients who withdraw from the study before completing the follow-up will be considered as failures.

A descriptive listing will present for each patient: the duration of nosebleeds before treatment, during treatment, after treatment, the treatment group, the number of consecutive days of treatment, the total number of days of treatment.

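### Tolerance is analysed without confidence intervals, and treatment stops of 8 or more days for an adverse reaction have no by-arm summary in the final analysis

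*Combined protocol and SAP*

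**What the plan says.** Section 3.2 lists first among the secondary objectives "Tolerance of tacrolimus nasal administration for 6 weeks, throughout the study". Section 2.2 says the safety of nasal use is not known.

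Section 9.2.2.5 plans the following for adverse events:

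- MedDRA coding, and then "Each adverse event observed between inclusion and the end of follow-up will be listed by frequency in each group".
- A between-arm comparison: "percentage of patients with at least one adverse event, or at least one severe adverse event will be computed and compared between the 2 groups". No test, significance level, confidence interval, margin or bound is given.
- "A list and verbatim of severe adverse events will be provided".
- The analysis set: "All analyses will be performed on the safety population". Section 9.2.1.3 defines this as everyone who received at least one application.

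The same section reports the percentage of patients with systemic absorption and lists exposure levels where the drug is detected.

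Section 2.3 treats "a cessation of treatment for at least 8 consecutive days, for safety concern", due to the ointment, as a major problem. The independent committee's step rules count these stops. In the final analysis, section 9.2.2.4 provides only a per-patient listing that includes treatment group, "the number of consecutive days of treatment, the total number of days of treatment". That listing does not give the reason for stopping.

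**The concern.** The documents say no tolerance data exist for this route, so the tolerance result is one of the main things the trial can contribute. A bare comparison of two percentages in 48 patients tends to be reported as a p-value. If it is not significant, readers may take the ointment to be tolerated as well as placebo, although the data may be compatible with a sizeable excess.

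The two compared measures also fit the question poorly. Any AE is blunt: section 1.3.3.1 reports, for skin use, that "Approximately 50% of patients experienced some type of skin irritation adverse reaction at the site of application", mostly mild and short-lived. The second measure is ambiguous, because section 4.3.2 expands SAE as severe adverse events while section 7.1.2 says a severe event need not be serious. A stop for an adverse reaction lasting at least 8 consecutive days is closer to what tolerance means here, yet it would have no estimate by arm at the end of the trial.

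**Working it through.** **Inputs from the documents.** Section 9.1: 24 per arm planned; sized on 60% v 15% improved, two-sided 5%, 80% power, Fisher exact test, 22 per arm before allowance for losses. Section 1.3.3.1: about 50% irritation with the active ointment on skin. No placebo AE rate, severe AE rate or stop rate is given.

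**Assumptions.** Two-sided Fisher test at 5%, borrowed from the primary analysis because section 9.2.2.5 names none; 24 per arm in the safety population; a range of event rates.

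**Method.** Power = Σ over all (a, b) of Bin(a; n, p_active) × Bin(b; n, p_placebo) × 1[Fisher p ≤ 0.05]. Miss rate = 1 − power.

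**Plan's own figure first.** For 60% v 15%, power is 0.797 at n = 20, 0.799 at n = 21 and 0.827 at n = 22. The stated 22 per arm reproduces. The design difference is 60 − 15 = 45 points, and it concerns efficacy only.

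**Miss rates at 24 per arm (placebo v active).**

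| Excess | Pair | Missed |
|---|---|---|
| 20 points | 0 v 20% | 46% |
| | 5 v 25% | 60% |
| | 10 v 30% | 69% |
| | 30 v 50% | 79% |
| | 50 v 70% | 79% |
| | 75 v 95% | 60% |
| 25 points | 0 v 25% | 25% |
| | 5 v 30% | 44% |
| | 10 v 35% | 54% |
| | 25 v 50% | 66% |
| | 35 v 60% | 67% |
| | 70 v 95% | 44% |

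So 20 points is missed 60-79% of the time for placebo rates of 5-75%, and 25 points 44-67% for placebo rates of 5-70%. Outside those limits, where one arm approaches 0% or 100%, the miss rate falls. If the 50% irritation figure is taken as the active rate, the misses are 79% (30 v 50%) and 66% (25 v 50%).

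**Sensitivity to the test.** With an uncorrected normal approximation, the ranges become 51-72% (20 points) and 37-59% (25 points). The excess detectable with 80% power under Fisher is about 34 points at a placebo rate of 5% and 43 points at 25-30%.

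**What intervals would show.** The Newcombe upper limit for d = p1 − p2 is d + √[(u1 − p1)² + (p2 − l2)²], where l and u are Wilson limits; the lower limit is analogous.

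- 12/24 v 12/24: Wilson limits 0.314 to 0.686, so √(0.186² + 0.186²) = 0.263. The interval is −26 to +26 points, with p = 1.
- 17/24 v 12/24: d = 21 points, p = 0.24, interval −6 to +44 points.
- 4/24 v 0/24: d = 17 points, p = 0.11, interval about 0 to 36 points.
- 0/24 in one arm: exact two-sided 95% upper limit 1 − 0.025^(1/24) = 14%.

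**Early discontinuation.** If inclusion ends at 24 patients (Step 3B), about 12 per arm, the miss rate for 50 v 75% rises from 66% to 86%.

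**Where the 8-day stop is and is not counted.** The step rules use data from the day-31 call for each new batch, plus end-of-treatment data for earlier batches. Only the first step compares arms by a fixed rule; later thresholds use the total count. No committee meeting is planned after the last 24 patients (Step 3A) or the last 16 (Step 4A). With treatment on days 1-42, a stop starting on days 24-35 reaches its eighth day on days 31-42, after the 30 days that the call covers. Neither 9.2.2.4 nor 9.2.2.5 tabulates these stops by arm.

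**The case against.** The strongest reply is that tolerance is a secondary objective in a 48-patient phase II trial sized for efficacy, so low power for AEs is expected and is not itself a fault. The plan already gives AE frequencies by arm, severe-event verbatims and an absorption percentage, and a reader with the counts could compute intervals. Section 9.2 says it holds only the main elements and may be revised before database freeze. The stops are also not ignored: they drive the step rules, and the listing shows treatment days by patient and group.

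Much of this stands, and it rules out several stronger readings:

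- A reader might infer that the comparison is the only tolerance output. It is not, although none of the other outputs carries an interval.
- A reader might infer that any 20-25 point excess is missed at least 60% of the time. That fails for 25 points at low placebo rates, which are plausible for severe events and safety stops: 44% at 5 v 30% and 25% at 0 v 25%.
- A reader might infer that a null result tells us nothing. It would still argue against an excess of about 40 points or more, and 1/24 in each arm would exclude an excess above about 16 points.
- A reader might infer that the plan will treat non-significance as proof of tolerance. It does not say so.

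What the reply does not supply is any planned interval, or a final by-arm count of stops for an adverse reaction. The listing omits the reason for stopping, and the step rules do not cover the last batch.

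**Conclusion.** The point holds as a gap in estimation and reporting, worth correcting before database freeze. Section 9.2.2.5 attaches no measure of precision to any tolerance result, and the event on which section 2.3 builds its inclusion rules has no final estimate by arm. At 24 per arm, a non-significant AE comparison is weak evidence of tolerance: about 60-79% of 20-point excesses and 44-67% of 25-point excesses would be missed at placebo rates of at least 5% (up to 75% and 70% respectively), and fewer near 0%. These figures rest on an assumed two-sided 5% Fisher test and assumed event rates, since the plan gives neither for adverse events. A less conservative test lowers them by roughly 7 to 9 points at the ends of the ranges. The need for intervals does not depend on the exact miss rate.

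**What to change.** In section 9.2.2.5, replace the unspecified comparison with estimation in the safety population. For each arm give the number and percentage with an exact (Clopper-Pearson) 95% interval, and give the active-minus-placebo risk difference with a Newcombe 95% interval, for:

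1. any AE;
2. severe AEs, defined by the intensity grades of section 7.1.3;
3. serious AEs as defined in section 7.1.2, kept separate from severe;
4. application-site reactions;
5. treatment stops of at least 8 consecutive days for an adverse reaction over the 6 weeks of treatment, stating how a permanent stop with fewer than 8 treatment days left is counted.

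Add a sentence that a non-significant difference will not be taken as evidence of equal tolerance, and that the tolerance conclusion will be worded from the intervals. No acceptability threshold is proposed here, because the documents give no basis for one.

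The cost is a few lines of SAP text and one table. The data are already collected: AE pages with action taken on study medication (section 7.2.1), dates and reasons for interruptions from the two calls (6.3, 6.4), and the daily administration boxes on the grids (6.2, Appendix 1). Sample size and visits are unchanged. The drawback is wide intervals, about ±26 points at mid-range rates, and a less favourable safety statement.

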4.3.2 Secondary judgement criteria

1. Adverse Events (AE) and Severe Adverse Events (SAE) observed throughout the study (clinical examination, epistaxis grids, ENT examination at each visit before and after the treatment). Additionally, all patients are contacted by phone after 15 and 30 days of treatment in order to collect data on tolerance and observance of the treatment.
2. Clinical efficacy criteria:
 - Nosebleed duration will be evaluated by the nosebleed monitoring grids completed by the patient (Appendix 1), collected at inclusion (V1): observation of the nosebleeds in the 6 weeks prior to inclusion, at the end of the treatment (V2): observation of the nosebleeds in the 6 weeks during treatment, and at the end of the study (V3): observation of the nosebleeds in the 6 weeks after the end of the treatment.
 - Progress in the number of nosebleeds. This criterion will be evaluated by the nosebleed monitoring grids completed by the patient (Appendix 1) collected at inclusion (V1): observation of the nosebleeds in the 6 weeks prior to inclusion, at the end of the treatment (V2): observation of the nosebleeds in the 6 weeks during treatment, and at the end of the study (V3): observation of the nosebleeds in the 6 weeks after the end of the treatment.
 - Comparison of the number of red blood cell transfusions between inclusion (V1) (collected over 6 weeks before treatment), the end of the treatment (V2) (collected over 6 weeks of treatment) and at the end of the study (V3) (collected over 6 weeks after the end of the treatment).
 - Progress in the scores obtained in the SF36 quality of life questionnaire

completed at inclusion (V1), at the end of the treatment (V2) and at the end of the study (V3).

- Progress in the ESS (Epistaxis Severity Score) using data from the specific questionnaire (Appendix 2) completed at inclusion (V1), at the end of the treatment (V2) and at the end of the study (V3).

Biological efficacy criteria: progress in hemoglobin and serum ferritin concentrations between inclusion (V1) and the end of the treatment (V2) and at the end of the study (V3).

3. Systemic absorption, after 1, 3 and 6 weeks of nasal administration, will be evaluated by a tacrolimus dosage in the blood at the end of the treatment.

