7.1.2 Serious adverse event (SAE)

A **serious adverse event** (SAE) is any untoward medical occurrence that at any dose:

- Results in death
- Is life-threatening (*the term "life-threatening" in the definition of "serious" refers to an event in which the patient was at risk of death at the time of the event ; it does not refer to an event which hypothetically might have caused death if it were more severe*)
- Requires in-patient hospitalization or prolongation of existing hospitalization
- Results in persistent or significant disability/incapacity
- Is a congenital anomaly/birth defect
- Is a medically significant event:

Medical and scientific judgment should be exercised in deciding whether expedited reporting is appropriate in situations, such as important medical events that may not be immediately life-threatening or result in death or hospitalization but may jeopardize the patient or may require intervention to prevent one of the outcomes listed in the definition above.

The term "severe" is a measure of intensity, thus a severe adverse event is not necessarily serious. For example, "nausea of several hours" duration may be severe but may not be clinically serious.

For "TACRO" study, any tacrolimus blood concentration resulting > 5ng/ml and any sign of infection under treatment should be considered as medically significant event and reported immediately by the investigator to the sponsor as a SAE.

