7.1.3 Intensity

The intensity of the event will be graded according to the following classification:

- Mild (grade 1): Discomfort noticed but no disruption of normal daily activity
- Moderate (grade 2): Discomfort sufficient to reduce or affect normal daily activity
- Severe (grade 3): Incapacitating with inability to work or perform normal daily activity
- Life-threatening (grade 4): Substantial risk of dying at time of event
- Death: (grade 5)

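### Section 9.2.2.5 orders the between-arm comparison and verbatim list for *severe* adverse events, which the protocol defines as different from *serious*, and no output is defined for serious events

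*Combined protocol and SAP*

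**What the plan says.** The safety paragraph of 9.2.2.5 has MedDRA coding for AEs and SAEs, a frequency listing of all adverse events by arm, and two further outputs. The first is the percentage of patients with any adverse event, or with "at least one severe adverse event will be computed and compared between the 2 groups". The second reads: "A list and verbatim of severe adverse events will be provided". All are on the safety population.

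Section 7.1.2 defines the SAE by the usual seriousness criteria and warns that the term severe "is a measure of intensity, thus a severe adverse event is not necessarily serious". Section 7.1.3 then fixes the term on the intensity scale: "Severe (grade 3): Incapacitating with inability to work or perform normal daily activity". Grades 4 (life-threatening) and 5 (death) have their own labels. Section 7.1.2 also adds two SAEs specific to this trial: "any tacrolimus blood concentration resulting > 5ng/ml and any sign of infection under treatment should be considered as medically significant event". Neither carries an intensity threshold.

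The abbreviation list expands SAE as serious. The criterion in 4.3.2 instead reads "Adverse Events (AE) and Severe Adverse Events (SAE) observed throughout the study", and the synopsis and the safety committee steps of 2.3 use the same expansion.

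**The concern.** *Severe* and *serious* are separate variables here. Section 7.2.1 requires an intensity for every adverse event, and 7.2.3 requires dedicated SAE pages. Whoever programs 9.2.2.5 can therefore build the table on either one and claim to follow the plan.

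The choice matters because of the two trial-specific SAEs. They are the signals of systemic exposure and immunosuppression, and they count whatever their intensity. Section 2.2 acknowledges that the safety of nasal administration is unknown, and tolerance is the first secondary objective. An SAE table built on intensity would not answer the question that 7.1.2 was written to raise.

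**Working it through.** The plan gives no figure on this point, so the check sets the definitions against the planned outputs.

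**Step 1: possible readings of *severe* in 9.2.2.5.**
- A: serious, as in 7.1.2 (treating *severe* as a slip for the S in SAE).
- B: grade 3 only, as labelled in 7.1.3.
- C: grade 3 or higher.

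**Step 2: what each reading puts into the comparison and the verbatim list.**

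| Event | SAE under 7.1.2? | A | B | C |
|---|---|---|---|---|
| Grade 1 or 2 sign of infection on treatment | Yes | In | Out | Out |
| Tacrolimus above 5 ng/mL, no symptoms | Yes | In | Out | Out |
| Grade 3 local burning meeting no seriousness criterion | No | Out | In | In |
| Grade 3 event leading to hospital admission | Yes | In | In | In |
| Event graded life-threatening (4) or fatal (5) | Yes | In | Out | In |

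The second row follows from how 7.1.3 is built. Grades 1 to 3 are described by discomfort and effect on daily activity, so a laboratory value without symptoms cannot reach grade 3. Readings B and C both lose the first two rows. Reading B, the literal one, also loses the last.

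**Step 3: where the omitted events would still appear.**
- Section 7.2.3 requires every SAE to be entered on the adverse event page as well. The events therefore enter the frequency listing by arm and the comparison of patients with at least one adverse event.
- The last paragraph of 9.2.2.5 gives the percentage of patients with systemic absorption and lists the level whenever tacrolimus is detected. This covers the second row, but it specifies no between-arm comparison and says nothing about infections.
- The frequency listing is not specified to show seriousness.

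**Step 4: what remains.** Under B or C, no specified output gives the percentage of patients with a serious event by arm, and no specified list gives the verbatim of low-grade SAEs (under B, nor of grade 4 and 5 events).

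**Step 5: a dependency.** Even under A, the infection count is not settled. Section 7.1.2 takes signs of infection on treatment without regard to cause, while 7.4.4 refers to infection attributed to immunosuppressive action. The two give different numerators.

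**The case against.** The strongest reply is that nobody would misread the section. It opens with AEs and SAEs as a pair and then names the same pair in words. The synopsis, 2.3 and 4.3.2 all expand SAE as *severe*, and 9.2.2.5 mentions no grade. The literal reading would exclude deaths, which no safety section can intend. The unit that builds the eCRF, with its SAE pages, also runs the analysis.

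As evidence of intent this stands: *serious* is probably meant. It does not cure the text. The protocol gives *severe* its own meaning and itself warns against equating the two words. Section 7.2.2 also has a separate reporting rule for grades 3 to 5, so a table by grade would not look out of place.

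Two stronger readings are tempting. A reader might infer that the analysis *will* tabulate grade 3 events; the documents support only that it *could*. A reader might also infer that the trial-specific SAEs would vanish from the report. They would not, because the all-event listing and the absorption output remain. SAE reporting to the sponsor uses *serious* correctly throughout section 7 and is unaffected.

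**Conclusion.** The wording of 9.2.2.5 is wrong by the protocol's own definitions and should be corrected. The consequence is limited: at risk are the between-arm percentage of patients with a serious event and the SAE verbatim list. The primary analysis, the sample size and data collection are untouched.

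The loss arises only if *severe* is applied as 7.1.3 defines it. The number of patients affected cannot be given, because the documents contain no rate of infection or raised tacrolimus level after nasal use. A reader might reach for the 26% skin infection rate in 1.3.3.1, but that comes from an open-label study of atopic dermatitis treated on the skin, described as a trial in children, and says nothing about the nasal route in adults with HHT. Nor do the documents support a claim that the trial-specific SAEs would mostly be low grade; the point needs only that they can be.

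**What to change.** - **Section 9.2.2.5:** in both the comparison and the list, replace *severe* by *serious (as defined in 7.1.2, including the two trial-specific events)*.
- **Expansion of SAE:** correct it to *serious* once in the synopsis, four times in 2.3 (Steps 1, 2A, 2B and 3C) and once in 4.3.2. With the two places in 9.2.2.5, that is 1 + 4 + 1 + 2 = 8 small edits.
- **Infection wording:** reconcile 7.1.2 with 7.4.4 so that the SAE numerator has one definition. While there, note that 7.1.2 sets its SAE threshold above 5 ng/mL, whereas 2.2 and 7.4.4 act from 5 ng/mL upward; these passages should also be reconciled.
- **Optional:** add a separate table of patients with an event of grade 3 or higher, by arm.

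The cost is a few words and at most one extra table from data already collected. Section 9.2 allows the analysis plan to be revised until the database is frozen; the edits to other sections follow the amendment route in 11.6.
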